10.7. Appendix 7: Reporting Standards for Missing Data

10.7.1. Premature Withdrawals

Element	Reporting Detail
General	
 Participant study completion (i.e. as specified in the protocol) was defined as completion of all phases of the study including the last study visit and the last scheduled procedure shown in the Schedule of Activities (Appendix 2) For the purposes of reporting, a participant is considered to have completed the study if they have not withdrawn and attended Visit 12 Withdrawn participants were not replaced in the study. All available data from participants who were withdrawn from the study will be listed and all available planned data will be included in summary tables and figures, unless otherwise specified. Withdrawal visits will be slotted as per Appendix 3: Assessment Windows or will be summarised as withdrawal visits.

10.7.2. Handling of Missing Data

Element	Reporting Detail
General	
 Missing data occurs when any requested data is not provided, leading to blank fields on the collection instrument: 
 These data will be indicated by the use of a “blank” in participant listing displays. Unless all data for a specific visit are missing in which case the data is excluded from the table. Answers such as “Not applicable” and “Not evaluable” are not considered to be missing data and should be displayed as such.
Outliers	
 If outliers are identified, analyses may be repeated excluding the outlying data Any participants excluded from the summaries and/or statistical analyses will be documented along with the reason for exclusion in the clinical study report.

10.7.2.1. Handling of Missing and Partial Dates

Element	Reporting Detail
General	
 Partial dates will be displayed as captured in participant listing displays.
Adverse Events	
 The eCRF allows for the possibility of partial dates (i.e., only month and year) to be recorded for AE start and end dates; that is, the day of the month may be missing. In such a case, the following conventions will be applied for calculating the time to onset and the duration of the event: 
 Missing Start Day: First of the month will be used unless this is before the start date of study treatment; in this case the study treatment start date will be used and hence the event is considered On-treatment as per Appendix 4: Study Phases and Treatment Emergent Adverse Events. Missing Stop Day: Last day of the month will be used, unless this is after the stop date of study treatment; in this case the study treatment stop date will be used. Completely missing start or end dates will remain missing, with no imputation applied. Consequently, time to onset and duration of such events will be missing.
Concomitant Medications/	
 Partial dates for any concomitant medications recorded in the CRF will be imputed using the following convention:

Element	Reporting Detail
Medical History	

○ If the partial date is a start date, a '01' will be used for the day and 'Jan' will be used for the month
○ If the partial date is a stop date, a '28/29/30/31' will be used for the day (dependent on the month and year) and 'Dec' will be used for the month.
● The recorded partial date will be displayed in listings.

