10.4.1.2. Study Phases for Event Data

Classification of an AE as having onset on-treatment will be made with reference to the study treatment start and stop dates and the event onset date. If the event onset date is missing, then the event will be considered on-treatment.

Study Phase	Definition
Pre-treatment	If onset date is prior to treatment start date Start Date < Study Treatment Start Date
On-treatment	If onset date is on or after treatment start date & on or before treatment stop date + 3 days. Study Treatment Start Date ≤ Start Date ≤ Study Treatment Stop Date + 3 days
Post-treatment	If onset date is after treatment stop date + 3 days. Start Date > Study Treatment Stop Date + 3 days

Note: assume on-treatment unless there is evidence to the contrary

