10.10.5. Safety Tables

Safety: Tables					
No.	Population	IDSL / Example Shell	Title	Programming Notes	Deliverable [Priority]
Adverse Events (AEs)					
3.1.	Safety	AE3	Summary of All Adverse Events by Preferred Term	ICH E3	SAC
3.2.	Safety	AE3	Summary of Common (>=5%) Adverse Events by Overall Frequency	ICH E3	SAC
3.3.	Safety	AE3	Summary All Drug-Related Adverse Events by Preferred Term	ICH E3	SAC
3.4.	Safety	AE15	Summary of Common (>=5%) Non-serious Adverse Events by Preferred Term (Number of Subjects and Occurrences)	FDAAA, EudraCT	SAC
Serious and Other Significant Adverse Events					
3.5.	Safety	AE16	Summary/Listing of Serious Adverse Events by Preferred Term [Number of Subjects and Occurrences]	FDAAA, EudraCT	SAC
3.6.	Safety	AE3	Summary of Pre-treatment Serious Adverse Events by Preferred Term		SAC
3.7.	Safety	AE3	Summary of On-treatment Serious Adverse Events by Preferred Term		SAC
3.8.	Safety	AE3	Summary/Listing of Adverse Events Leading to Permanent Discontinuation of Study Treatment or Withdrawal from Study by Preferred Term	IDSL	SAC
3.9.	Safety		Summary/Listing of On-treatment Adverse Events of Special Interest		SAC
Laboratory: Chemistry					

Safety: Tables					
No.	Population	IDSL / Example Shell	Title	Programming Notes	Deliverable [Priority]
3.10.	Safety	LB1	Summary of Chemistry Changes from Baseline	ICH E3	SAC
3.11.	Safety	LB17	Summary/Listing of Worst Case Chemistry Results by Potential Clinical Importance Criteria (Post-Baseline Relative to Baseline)	ICH E3	SAC
Laboratory: Haematology					
3.12.	Safety	LB1	Summary of Haematology Changes from Baseline	ICH E3	SAC
3.13.	Safety	LB17	Summary/Listing of Worst Case Haematology Results by Potential Clinical Importance Criteria (Post-Baseline Relative to Baseline)	ICH E3	SAC
Laboratory: Hepatobiliary (Liver)					
3.14.	Safety	LIVER1	Summary of Liver Monitoring/Stopping Event Reporting	IDSL	SAC
3.15.	Safety	LIVER10	Summary/Listing of Hepatobiliary Laboratory Abnormalities	IDSL	SAC
ECG					
3.16.	Safety	EG1	Summary of ECG Findings	IDSL	SAC
3.17.	Safety	EG10	Summary/Listing of Maximum QTc Values Post-Baseline Relative to Baseline by Category	IDSL	SAC
3.18.	Safety	EG2	Summary of Change from Baseline in ECG Values by Visit	IDSL	SAC
3.19.	Safety	EG11	Summary/Listing of Maximum Increase in QTc Values Post-Baseline Relative to Baseline by Category	IDSL	SAC
Vital Signs					

Safety: Tables					
No.	Population	IDSL / Example Shell	Title	Programming Notes	Deliverable [Priority]

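### The rules for partial adverse event dates make events from a calendar month before first dose on-treatment, and can end an event before it starts

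*SAP*

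**What the plan says.** Section 10.7.2.1 covers AEs whose month and year are recorded but whose day is missing. It introduces its conventions as serving time to onset and duration.

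- **Missing start day:** "First of the month will be used unless this is before the start date of study treatment". Otherwise the treatment start date is used, and the same sentence concludes that the event is on-treatment, citing Appendix 4.
- **Missing stop day:** "Last day of the month will be used, unless this is after the stop date of study treatment". Otherwise the treatment stop date is used. There is no check against the AE's own start.

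Section 10.4.1.2, in Appendix 4, sets the phases. Pre-treatment applies "If onset date is prior to treatment start date". On-treatment applies "If onset date is on or after treatment start date & on or before treatment stop date + 3 days". Later onsets are post-treatment. A closing note says to "assume on-treatment unless there is evidence to the contrary". The treatment-emergent flag in 10.4.1.3 uses the same window as on-treatment.

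Three tables in 10.10.5 name a phase in their titles: 3.6 ("Summary of Pre-treatment Serious Adverse Events by Preferred Term"), 3.7 ("Summary of On-treatment Serious Adverse Events by Preferred Term") and 3.9 ("Summary/Listing of On-treatment Adverse Events of Special Interest").

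**The concern.** Moving an unknown day to first dose is a reasonable cautious convention when the event may have begun on either side of first dose. That is the position only in the month of first dose. The rule as written also catches every earlier month, where the recorded month alone shows that onset was pre-treatment. It likewise ignores a known AE end date before first dose. Either fact is evidence to the contrary in the sense of the note in 10.4.1.2, so the imputation overrides information that the phase rule says should decide.

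After early termination, Table 1 of the SAP gives safety as the primary interest. In a small study, one misplaced serious event or pneumonia would be visible in Tables 3.6, 3.7 or 3.9. Time to onset would also be wrong for such an event.

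The stop-day rule has a separate fault. It ties the end of the event to the end of treatment, although 10.4.1.2 expects onsets after treatment stop, and it shortens events that continue past treatment stop.

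**Working it through.** The SAP gives no figure to reproduce, so the rules are applied literally. The calendar dates below are illustrative. The SAP gives no formula for AE duration; I assume end − start + 1, the form that 10.6.2 uses for exposure.

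**Start day, by logic.** Let F be the first of the recorded month and T the first-dose date.
- If F < T, the imputed onset is T, which is not before T.
- If F ≥ T, the imputed onset is F, which is not before T.

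Pre-treatment needs onset < T, so no AE with a missing start day can be pre-treatment.

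**Start day, examples with T = 20 April.**

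| Recorded AE | Imputed start | End used | Duration | Correct phase | Phase assigned |
|---|---|---|---|---|---|
| March (no day) to March (no day) | 20 April | 31 March | −20 + 1 = −19 | pre-treatment | on-treatment |
| April (no day) to 5 April | 20 April | 5 April | −15 + 1 = −14 | pre-treatment | on-treatment |
| April (no day), no earlier end known | 20 April | n/a | n/a | uncertain | on-treatment (defensible) |

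**How much of screening lies in an earlier calendar month.** Sections 2.3 and 10.2.1 allow screening up to 32 days before Day 1. If Day 1 falls on day j of a month, then max(0, L − j + 1) of the preceding L days lie in an earlier month. Sum this over a 365-day year and divide by 365 × L:

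- L = 32: a 31-day month contributes 527, a 30-day month 525 and February 518. The total is 7 × 527 + 4 × 525 + 518 = 6,307, and 6,307 / 11,680 = 54.0%.
- L = 28: 12 × 406 / 10,220 = 47.7%.
- L = 21: 12 × 231 / 7,665 = 36.2%.
- L = 14: 12 × 105 / 5,110 = 24.7%.
- L = 7: 12 × 28 / 2,555 = 13.2%.

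These are shares of days, not of events. They show only that an earlier month is an ordinary occurrence within the screening window.

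**Stop day.** Let E be treatment stop and let the AE start on E + k, with k ≥ 1. The last day of its end month is on or after E + k, hence after E, so the cap always applies and the end becomes E. Duration = E − (E + k) + 1 = 1 − k:

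- k = 1, 2, 3 (on-treatment under 10.4.1.2): 0, −1, −2 days.
- k = 28 (the follow-up limit in 2.3): −27 days.

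The end precedes the start for every k.

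**Truncation.** Take onset 5 June, treatment stop 10 June and end recorded as July without a day. The rule gives 10 June − 5 June + 1 = 6 days. The earliest end consistent with the record is 1 July, which gives 26 + 1 = 27 days.

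**The case against.** The best defence is that the two sections do not formally clash. Section 10.4.1.2 classifies by onset date, and 10.7.2.1 supplies that date when the day is missing. Once onset is set to first dose, the on-treatment definition is met. An analyst who reads the note in 10.4.1.2 alongside the rule could also treat an earlier month as contrary evidence. Leaning towards on-treatment is plainly intended, since an AE with no onset date at all is also counted there.

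Part of this stands. The lean is sound in the month of first dose when nothing else is known, and the fault can be described as a missing qualifier. But 10.7.2.1 states the on-treatment result outright and leaves no room for the note, so a programmer following it will misclassify the event.

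The limits on reach also stand. Only Tables 3.6, 3.7 and 3.9 name a phase in their titles. No listed summary table names duration or time to onset. Listings show the partial date as recorded, and the rule is the same in both arms. No formal analysis is planned. Which events are collected before first dose is a protocol matter not visible here, and it could narrow the reach further.

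**Conclusion.** The concern holds, as a minor one. The start-day rule gives a demonstrably wrong phase for any AE recorded in a calendar month wholly before first dose, and for any AE with a known end before first dose. It can move serious events from Table 3.6 to Table 3.7 and add pre-treatment pneumonia events to Table 3.9, because 10.6.4 defines the events of special interest as infective pneumonia. The stop-day rule sets the end before the start for every AE that begins after treatment stop and lacks an end day. Its effect is confined to derived duration.

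The number of affected events cannot be given, because the SAP does not say how many AEs have a missing day; it may be none. The negative durations assume the inclusive day count; without the added day each would be one lower. The ordering fault does not depend on that choice.

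**What to change.** Replace the two sentences in 10.7.2.1:

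- **Missing start day:** use the treatment start date only if the recorded month and year are those of treatment start and no known AE end date precedes treatment start. Otherwise use the first of the month.
- **Missing stop day:** use the last day of the month, or the date of death or last contact if earlier, but never a date before the AE start. Do not cap at treatment stop. The limit at death or last contact is a sensible refinement; the essential parts are dropping the cap and keeping the end on or after the start.

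On the examples above, March becomes 1 March (pre-treatment), April ending on 5 April becomes 1 April (pre-treatment), and April with no earlier end stays at 20 April (on-treatment).

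The cost is two sentences and the matching date-derivation code, with no new tables. The cautious default is kept where the date is truly ambiguous, so there is no material downside.

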10.8. Appendix 8: Values of Potential Clinical Importance

10.8.1. Laboratory Values

The following table identifies a range of potential clinical importance (PCI) for each laboratory analyte. Limits with an 'x' are multipliers of the central laboratory normal range. Values above and below this range will be considered of PCI.

Haematology Analyte (units)	Effect	COPD Patients	
		Low	High
Platelet Count (x10 ⁹ /L)		0.90x	1.10x
Red Blood Cell Count (x10 ¹² /L)		0.93x	1.07x
White Blood Cell Count (x10 ⁹ /L)		0.70x	1.60x
Reticulocyte Count (%)			>4%
Haemoglobin (g/L)	Males	0.85x	1.20x
	Females	0.85x	1.20x
Hematocrit (Ratio of 1)	Males	0.50x	1.30x
	Females	0.50x	1.30x
MCV (fL)		0.25x	2.00x
MCH (pg)		0.85x	1.20x
MCHC (g/dL)		0.85x	1.10x
Neutrophils (%)		0.65x	1.50x
Lymphocytes (%)		0.80x	1.20x
Monocytes (%)		0.80x	1.60x
Eosinophils (%)			2.00x
Basophils (%)			5.00x

Note: Multipliers are identified by "x", otherwise actual comparison values are provided with units.

Chemistry Analyte	Effect	COPD Patients	
		Low	High
BUN (mmol/L)		0.70x	1.60x
Creatinine (μmol/L)			1.30x (or >27 μmol/L increase from baseline)
Glucose fasting (mmol/L)		<0.6x	>4x
Sodium (mmol/L)		0.80x	1.15x
Potassium (mmol/L)		0.75x	1.30x
Chloride (mmol/L)		0.90x	1.10x
Bicarbonate (mmol/L)		<18 mmol/L	>32 mmol/L
Calcium (mmol/L)		0.85x	1.08x
GGT (U/L)		0.85x	1.10x
Uric Acid (mg/dL)	Males	<2.1 mg/dL	>8.5 mg/dL
	Females	<2.0 mg/dL	>7.0 mg/dL
Albumin (mmol/L)		0.90x	1.50x
Total Protein (mg/dL)			1.25x

Note: Multipliers are identified by “x”, otherwise actual comparison values are provided with units.

Liver Function Test Analyte	Effect	PCI Range	Unit
ALT/SGPT	High	≥ 3x ULN	U/L
AST/SGOT	High	≥ 3x ULN	U/L
Alkaline Phosphatase	High	≥ 2x ULN	U/L
Total Bilirubin	High	≥ 2x ULN	μmol/L
Direct Bilirubin	High	≥ 2x ULN	μmol/L
Total Bilirubin + ALT	High	≥ 2x ULN Total Bilirubin + ≥ 3x ULN ALT	μmol/L U/L

10.8.2. ECG

ECG Parameter	PCI Range	Unit
Absolute QTc Interval (QTcB, QTcF)	>530	msec
Increase from Baseline QTcB,QTcF	>60	msec
QT Interval	<300 or >500	msec
PR Interval	<120 or >240	msec
QRS Interval	<70 or >125	msec
RR Interval	<375 or >1714	msec
Heart Rate	<35 or >120	bpm

10.8.3. Vital Signs

Vital Sign Parameter	PCI Range	Unit
Systolic BP	<90 or >160	mmHg
Diastolic BP	<40 or >110	mmHg
Heart Rate	<35 or >120	bpm
Respiration Rate	<8 or >30	breaths /min

10.9. Appendix 9: Abbreviations & Trade Marks

10.9.1. Abbreviations

Abbreviation	Description
AE	Adverse Event
AESI	Adverse Event of Special Interest
ATC	Anatomical Therapeutic Chemical Classification
BD	Bronchodilator
BP	Blood Pressure
BUN	Blood urea nitrogen
CAT	COPD Assessment Test
COPD	Chronic Obstructive Pulmonary Disease
CSR	Clinical Study Report
DBF	Database Freeze
DBR	Database Release
DP	Decimal Places
ECG	Electrocardiogram
eCRF	Electronic Case Record Form
EW	Early Withdrawal
EudraCT	European Clinical Trials Database
FDA	Food and Drug Administration
FDAAA	Food and Drug Administration Clinical Results Disclosure Requirements
FEV ₁	Forced Expiratory Volume in 1 Second
FVC	Forced Vital Capacity
GGT	Gamma-glutamyl transferase
GOLD	Global Initiative for Obstructive Lung Disease
GSK	GlaxoSmithKline
HCRU	Healthcare Resource Utilization
IDSL	Integrated Data Standards Library
ICH	International Conference on Harmonization
MCH	Mean corpuscular hemoglobin
MCHC	Mean corpuscular hemoglobin concentration
MCV	Microtic cell volume
MDI	Metered Dose Inhaler
MedDRA	Medical Dictionary for Regulatory Activities
MMRM	Mixed Model Repeated Measures
NQ	Non-quantifiable
PCI	Potential Clinical Importance
PD	Protocol Deviations
QTcF	Frederica's QT Interval Corrected for Heart Rate
QTcB	Bazett's QT Interval Corrected for Heart Rate
RAP	Reporting & Analysis Plan
RMC	Respiratory Medication Class
SAC	Statistical Analysis Complete
SAE	Serious Adverse Event

Abbreviation	Description
SD	Standard Deviation
SGOT	Serum glutamic oxaloacetic transaminase
SGPT	Siamane glutamate pyruvate transaminase
SGRQ	St. George's Respiratory Questionnaire
SGRQ-C	SGRQ for COPD patients
SMQ	Standardized MedDRA Query
ULN	Upper limit of normal

10.9.2. Trademarks

Trademarks of the GlaxoSmithKline Group of Companies
None

Trademarks not owned by the GlaxoSmithKline Group of Companies
SAS
ERT

10.10. Appendix 10: List of Data Displays

10.10.1. Data Display Numbering

The following numbering will be applied for RAP generated displays:

Section	Tables	Figures
Study Population	1.1 to 1.24	
Efficacy	2.1 to 2.15	
Safety	3.1 to 3.21	3.1 to 3.3
Section	Listings	
ICH Listings	1 to 37	

10.10.2. Deliverables

In all displays the term "Subjects" is used to refer to "Participants".

Delivery	Description
SAC	Final Statistical Analysis Complete

10.10.3. Study Population Tables

Study Population Tables					
No.	Population	IDSL / Example Shell	Title	Programming Notes	Deliverable [Priority]
Subject Disposition					
1.1.	Safety	ES1	Summary of Subject Disposition for the Subject Conclusion Record	ICH E3, FDAAA, EudraCT	SAC
1.2.	All subjects	ES6	Summary of Screening Status and Reasons for Screen Failure	Journal Requirements Specify Reasons for Screening Failure and include Reasons for Run-in Failure Section	SAC
1.3.	Safety	SD1	Summary of Treatment Status and Reasons for Discontinuation of Study Treatment	ICH E3 Required for all studies except single dose studies	SAC
1.4.	Safety		Summary of Attendance at Each Clinic Visit	Including Screening	SAC
Protocol Deviation					
1.5.	Safety	DV1	Summary of Important Protocol Deviations	ICH E3	SAC
1.6.	All subjects	IE2	Summary of Inclusion/ Exclusion/ Randomization Criteria Deviations for Screen or Run-in failures	Add a row "Number of Screen Failures" above "any criteria deviations". Percentage will be based on number of screen failures	SAC
1.7.	Safety	IE1	Summary of Inclusion/ Exclusion/ Randomization Criteria Deviations for the Safety Population		SAC
Population Analysed					

Study Population Tables					
No.	Population	IDSL / Example Shell	Title	Programming Notes	Deliverable [Priority]
1.8.	All Subjects	SP1	Summary of Study Populations	IDSL	SAC
Demographic and Baseline Characteristics					
1.9.	Safety	DM1	Summary of Demographic Characteristics	ICH E3, FDAAA, EudraCT	SAC
1.10.	Safety	DM5	Summary of Race and Racial Combinations	ICH E3, FDA, FDAAA, EudraCT	SAC
1.11.	Safety	SU1	Summary of Smoking History and Smoking Status	Include smoking status, smoking pack years, cigarettes smoked/day	SAC
1.12.	Safety	SP_T12	Summary of COPD History at Screening		SAC
1.13.	Safety	SP_T1	Summary of HCRU Exacerbation History at Screening	See notes in Section 10.6.2 Include subgroups of Mild, Moderate, Severe, and Moderate/Severe	SAC
1.14.	Safety		Summary of GOLD Stages at Screening	GOLD 1-4 and GOLD A-D	SAC
1.15.	Safety		Summary of Screening Spirometry Measures	Pre-BD FEV ₁ (L), Post-BD FEV ₁ (L), Predicted normal FEV ₁ (L), Percent predicted normal post-BD FEV ₁ (%), Post-BD FVC (L), Post-BD FEV ₁ /FVC	SAC
Past and Current Medical History					
1.16.	Safety	MH4	Summary of Past Medical Conditions	ICH E3	SAC
1.17.	Safety	MH4	Summary of Current Medical Conditions		SAC
Prior and Concomitant Medications					

Study Population Tables					
No.	Population	IDSL / Example Shell	Title	Programming Notes	Deliverable [Priority]
1.18.	Safety	CM1	Summary of Non-COPD Concomitant Medications	ICH E3	SAC
1.19.	Safety	CM8	Summary of COPD Concomitant Medications Taken Pre-treatment		SAC
1.20.	Safety	CM8	Summary of COPD Concomitant Medications Taken On-Treatment, Medications Given for Reasons Other than an Exacerbation		SAC
1.21.	Safety	CM8	Summary of COPD Concomitant Medications Taken Post-treatment		SAC
1.22.	Safety	CM8	Summary of On-treatment COPD Concomitant Medications Given for an Exacerbation		SAC
1.23.	Safety		Summary of COPD Concomitant Medication Categories Taken at Screening	Number and percentage of participants taking each medication in the RMC categories defined in section 10.6.2	SAC
Exposure					
1.24.	Safety	EX1	Summary of Exposure to Study Treatment	ICH E3	SAC

10.10.4. Efficacy Tables

Efficacy: Tables					
No.	Population	IDSL / Example Shell	Title	Programming Notes	Deliverable [Priority]
Spirometry					
2.1.	Safety	Based on PD4	Summary of Baseline Spirometry Measures	Post-BD FEV ₁ (L), Percent predicted normal post-BD FEV ₁ (%), Post-BD FVC (L), Post-BD FEV ₁ /FVC Transpose PD4 table to have treatment in columns and spirometry assessments in rows	SAC
2.2.	Safety	PD4	Summary of Post-Bronchodilator FEV ₁ (L)	Include raw and change from baseline	SAC
2.3.	Safety	PD4	Summary of Post-Bronchodilator FVC (L)	Include raw and change from baseline	SAC
SGRQ					
2.4.	Safety	PD4	Summary of Baseline SGRQ Scores	Total and domain scores	SAC
2.5.	Safety	PD4	Summary of SGRQ Scores by Visit	Include raw and change from baseline Total and domain scores	SAC
CAT					
2.6.	Safety	PD4	Summary of Baseline CAT Scores	Include total column	SAC
2.7.	Safety	PD4	Summary of CAT Score by Visit	Include raw and change from baseline	SAC
Rescue Medication Use					
2.8.	Safety	PD4	Summary of Baseline Mean Number of Puffs of Rescue Medication per Day using Diary Data	Include total column	SAC
2.9.	Safety	PD4	Summary of Baseline Percentage Rescue-free Days using Diary	Include total column	SAC

			Data		
2.10.	Safety	PD4	Summary of Mean Number of Puffs of Rescue Medication per Day using Diary Data in 4-week intervals		SAC
2.11.	Safety	PD4	Summary of Percentage Rescue-free Days using Diary Data in 4-week intervals		SAC
2.12.	Safety	PD4	Summary of Baseline Mean Number of Occasions of Rescue Use per Day using MDI Sensor Data	Include total column	SAC
2.13.	Safety	PD4	Summary of Baseline Percentage Rescue-free Days using MDI Sensor Data	Include total column	SAC
2.14.	Safety	PD4	Summary of Mean Number of Occasions of Rescue Use per Day using MDI Sensor Data in 4-week intervals		SAC
2.15.	Safety	PD4	Summary of Percentage Rescue-free Days using MDI Sensor Data in 4-week intervals		SAC

